3.1.5 Part B: Safety Expansion Phase (Not applicable)

No longer applicable.

Figure 1 Study flow chart

Part A – Dose Escalation Phase

[figure not shown]

Table 1 Study plan (Part A)

Visit	1	2	3	4	5	6	7	Follow up visits			Withdrawal from treatment ^a	
Visit Description	Screening visit	Start Tx	Tx	Tx	Tx	Tx	Tx	Tx	Tx	Tx	Tx stopped	30 days post last dose
Day	-14 to 0	1	8	15	22	29	36	57	NA	NA		
Week	-2 to 0	0	1	2	3	4	5	8	+ 4^a	+ 8^a		
Visit Window^b (visit date ± No. Days)	NA	NA	± 2 days	± 2 days	± 2 days	± 2 days	± 2 days	± 2 days	± 2 days	± 2 days	NA	NA
Informed consent	X											
Demography, Height, WHO performance status	X											
Medical history/Surgical history/smoking status	X											
Inclusion/exclusion criteria	X	X										
Pregnancy test (females) ^d	X	X ^c						X ^d		X ^d		
Physical examination	X	X	X	X	X	X	X	X ^a		X ^a	X	
Vital signs incl weight, and O ₂ Saturation ^c measurement	X	X	X	X	X	X	X	X	X	X	X	
ECG	X ^f	X ^g			As required						X ^e	
Clinical chemistry including BNP, Haematology, Coagulation ^h	X	X ^c	X	X	X	X	X	X	X	X	X	
Urinalysis	X	X ^c	X	X	X	X	X	X	X	X	X	
RECIST evaluation	X ⁱ							X ^j		X ^j		
Chest X-ray ^k	X	As required										
MUGA scan/Echo ^l	X	As required					X	As required				
Ophthalmologic exam ^m	X	As required					X	As required				
PK Blood samples ⁿ		X		X	X	X						

Table 1 Study plan (Part A)

Visit	1	2	3	4	5	6	7	Follow up visits			Withdrawal from treatment ^a	
Visit Description	Screening visit	Start Tx	Tx	Tx	Tx	Tx	Tx	Tx	Tx	Tx	Tx stopped	30 days post last dose
Day	-14 to 0	1	8	15	22	29	36	57	NA	NA		
Week	-2 to 0	0	1	2	3	4	5	8	+ 4^a	+ 8^a		
Visit Window^b (visit date ± No. Days)	NA	NA	± 2 days	± 2 days	± 2 days	± 2 days	± 2 days	± 2 days	± 2 days	± 2 days	NA	NA
PBMC blood sample ^o		X										
Optional blood sampling for host genetics research ^p		X										
Concomitant medication	X	X	X	X	X	X	X	X	X	X	X	X
Adverse events		X	X	X	X	X	X	X	X	X	X	X
Dispense study medication/check returned medication			X				X	X	X			
Diary card completion		X	X	X	X	X	X					
Part A only: Wash-out period		Days 2 to 7										

^a Patients to attend clinic visits every 4 weeks until withdrawal from treatment (relative to Day 1). A physical examination will be performed every 8 weeks (relative to Day 1).

^b Visit window is compared to baseline (Day 1).

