6.5 Determination of sample size

Part A of the study is not formally powered but is designed to provide adequate tolerability, safety, pharmacokinetic, and pharmacodynamic data.

Part A is also designed to ensure at least 6 evaluable patients are recruited at the dose deemed to be MTD.

The number of patients has been based on both feasibility and obtaining adequate data to assess the biological activity of AZD8330 in tumour in terms of the biomarker pERK in tumour, based on average within-patient reduction in pERK from baseline, as measured using semi-quantitative IHC methods.

Average reductions of 83% on pERK were observed in the first in man study with the MEK inhibitor AZD6244 ([Adjei A et al 2006](#)). The within patient standard deviation of the change from baseline (on the log scale) from this study is estimated as 2.2. 10 patients would therefore provide 80% power to detect an average 70% reduction at the 1-sided 20% significance level.

Therefore approximately 10 evaluable patients at each dose level are considered reasonable to indicate the possibility of biological activity.

The expansion also provides an opportunity to provide a better estimate of the tolerability of each dose for onward development. Expanding the cohort at the maximum tolerated dose from the dose escalation to around 20 provides a stronger estimate of the true DLT rate. For example if the MTD cohort had only 6 patients then:

- If 0 out of 6 DLTs are observed it can be concluded that the true DLT rate is less than 30% with 90% confidence.
- If 1 DLT (16.7%) is observed it can be concluded that the true DLT rate is less than 50% with 90% confidence.

However, with an additional 18 evaluable patients for example:

- If 0 out of 24 DLTs are observed it can be concluded that the true DLT rate is less than 10% with 90% confidence.
- If 4 out of 24 DLTs (16.7%) are observed it can be concluded that the true DLT rate is less than 32% with 90% confidence.

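### Section 6.5 supports the sample size with DLT-rate precision from an MTD expansion that the current protocol has removed

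*Protocol*

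**What the plan says.** Section 6.5 gives four statements about the true DLT rate at the MTD, each at 90% confidence and without naming an interval method.

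- Six patients, no DLT: "If 0 out of 6 DLTs are observed it can be concluded that the true DLT rate is less than 30% with 90% confidence".
- Six patients, one DLT: "If 1 DLT (16.7%) is observed it can be concluded that the true DLT rate is less than 50% with 90% confidence".
- 24 patients, no DLT: "If 0 out of 24 DLTs are observed it can be concluded that the true DLT rate is less than 10% with 90% confidence".
- 24 patients, four DLTs: "If 4 out of 24 DLTs (16.7%) are observed it can be concluded that the true DLT rate is less than 32% with 90% confidence".

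The figure of 24 comes from six patients plus more: "However, with an additional 18 evaluable patients for example". The argument that joins the two pairs is "Expanding the cohort at the maximum tolerated dose from the dose escalation to around 20 provides a stronger estimate of the true DLT rate".

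The rest of the current edition describes a different design. The heading of Section 3.1.5 reads "Part B: Safety Expansion Phase (Not applicable"). The synopsis and Section 3.1.1 describe a single part with 6 to 9 patients per cohort. Section 3.1.4.1 stops recruitment to a cohort once the Safety Review Committee has called its dose tolerated or non-tolerated. Section 6.5 itself commits only to a minimum of six evaluable patients at the MTD.

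**The concern.** Part A exists to define the MTD, and Section 6.5 holds the protocol's only figures for how precisely the DLT rate at that dose will be estimated. The more reassuring pair of figures belongs to a cohort that this design cannot produce. An ethics committee or investigator reading the section alone would conclude that a clean result at the MTD could limit the DLT rate to 10%, or that an observed rate of 16.7% could limit it to 32%. Neither is attainable. The protocol gives no bounds at all for 7, 8 or 9 patients, and Section 6.1 says that no separate SAP will be prepared, so the correct figures have no other obvious home.

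**Working it through.** **Can any cohort reach 20 or 24?** Cohorts hold 6 to 9 patients (synopsis; Sections 3.1.1 and 3.1.4.1). A classified cohort is closed (Section 3.1.4.1). Replacement patients are allowed only until the minimum evaluable number is reached (Sections 3.1.4 and 3.5). Part B is gone (Section 3.1.5). No route is left to 20 or 24 evaluable patients at one dose.

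**Method.** For x DLTs in n patients, the exact (Clopper-Pearson) one-sided 90% upper limit U solves P(X ≤ x | n, U) = 0.10. Equivalently, U is the 0.90 quantile of Beta(x+1, n−x). For x = 0 this reduces to U = 1 − 0.10^(1/n).

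**The plan's own figures.** The exact confidence attached to a stated bound b is 1 − P(X ≤ x | n, b).

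| Outcome | Stated bound | Exact 90% limit | Exact confidence at stated bound |
|---|---|---|---|
| 0/6 | 30% | 31.9% | 1 − 0.7^6 = 88.2% |
| 1/6 | 50% | 51.0% | 1 − 7/64 = 89.1% |
| 0/24 | 10% | 9.2% | 1 − 0.9^24 = 92.0% |
| 4/24 | 32% | 30.6% | 92.3% |

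All four stated bounds lie within 2 percentage points of the exact limits, and the 24-patient statements are slightly conservative. The upper ends of two-sided 90% Wilson intervals are 31.1%, 50.2%, 10.1% and 32.4%, close to all four. That may be their source, but the protocol does not say.

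**What the current design can deliver.** Section 3.1.4.1 classes a dose as tolerated with at most 1/6, 1/7, 2/8 or 2/9 patients having a DLT. Exact one-sided 90% upper limits:

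| n | Best case | Limit | Largest tolerated count | Limit |
|---|---|---|---|---|
| 6 | 0/6 | 31.9% | 1/6 | 51.0% |
| 7 | 0/7 | 28.0% | 1/7 | 45.3% |
| 8 | 0/8 | 25.0% | 2/8 | 53.8% |
| 9 | 0/9 | 22.6% | 2/9 | 49.0% |

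**Comparison.** With no DLTs, the best attainable limit is 22.6% against the 10% in the text, more than twice as high. At an observed rate of 16.7%, 1/6 gives 51.0% where 4/24 gives 30.6% by the same method, a difference of 51.0 − 30.6 = 20.4 points. The other boundary outcomes have different observed rates (14.3%, 25.0% and 22.2%), so they show the range of the design and are not like-for-like with 4/24.

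**The case against.** The strongest reply is that nothing operational depends on these figures. Escalation and the MTD rest on observed DLT counts and on the Safety Review Committee's judgement, Part A is not formally powered, and no hypothesis is tested. The one-part design is stated clearly elsewhere, so no site would open an expansion because of Section 6.5. The 24-patient bounds are also valid numbers for 24 patients. All of this stands, and it limits the seriousness of the point. It does not rescue the text, which still offers precision from patients who will not be enrolled.

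A reader might go further and infer that the six-patient bounds are arithmetical errors that oversell the design. The documents do not support that. No method is named, and the gaps under the exact method are 1.9 and 1.0 percentage points. One-sided 90% Wilson (21.5%, 42.5%), mid-p (23.5%, 44.4%) and uniform-prior Bayesian (28.0%, 45.3%) limits all satisfy the stated bounds. Those bullets were also written to show how little six patients can tell, and a bound of 50% for 1/6 already conveys that.

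A reader might also see a contradiction between about 20 patients and 6 + 18 = 24. The first number is approximate and the second is offered as an example. The exact limit for 0/20 is 10.9%, but the section never attaches the 10% bound to 20 patients.

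**Conclusion.** The point holds as an internal inconsistency. Section 6.5 supports the sample size with DLT-rate precision that the current design cannot reach. A dose can be classed as tolerated while the exact one-sided 90% upper limit for its DLT rate is between 45.3% and 53.8%, and even a clean cohort of nine leaves 22.6%. The text offers 32% and 10%. The recomputed limits assume independent patients with a common DLT rate, a fixed cohort size and the Clopper-Pearson method; another method would shift them somewhat. That 20 or 24 patients are out of reach does not depend on the method. The difference between 30% and 31.9%, and between 50% and 51.0%, is a minor matter of method and rounding. The section should be corrected at the next amendment, but the error does not affect dose decisions or the analyses.

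**What to change.** In Section 6.5, delete the expansion paragraph and the two 24-patient bullets. Restate the DLT-rate precision for the cohorts actually planned, at 6, 7, 8 and 9 patients, covering at least the zero-DLT result and the largest count still classed as tolerated. Name the interval method and say that the limits are one-sided. The second table under the working can serve if the exact method is chosen. As a tidy-up under that choice, the six-patient bounds become about 32% (0/6) and 51% (1/6).

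The cost is a text change. The stated precision becomes less favourable. No extra patients are needed, and no escalation or MTD rule changes.

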6.6 Interim analyses

No formal statistical interim analysis will be undertaken.

6.7 Data monitoring board (Not applicable)

Not applicable to this Study.

6.8 Study Safety Review Committee

A study Safety Review Committee will meet during Part A following each dose step (ie, following one cycle of treatment for each dose level). The Safety Review Committee comprising of the Investigators, the Medical Science Director, the Study Team Physician, the Pharmacokineticist and the Global Drug Safety Physician (or nominated deputy in each case) will assess the available safety, tolerability and PK data. The committee must include a minimum of 3 physicians at least 1 of who must be an investigator, but may also include other team members, if appropriate (eg, statistician etc).

Further details of the Safety Review Committee can be found in the Safety Review Committee Guidelines.

7. STUDY MANAGEMENT

7.1 Monitoring

Before first subject into the study, a representative of AstraZeneca will visit the investigational study site to:

- Determine the adequacy of the facilities.
- Discuss with the investigator(s) (and other personnel involved with the study) their responsibilities with regard to protocol adherence, and the responsibilities of

AstraZeneca or its representatives. This will be documented in a Clinical Study Agreement between AstraZeneca and the investigator.

- Discuss the specific requirements of the genetic research with the investigator(s) (and other personnel involved with the study).
- During the study, a monitor from AstraZeneca or company representing AstraZeneca will have regular contacts with the study site, including visits to:
- Provide information and support to the investigator(s).
- Confirm that facilities remain acceptable.
- Confirm that the investigational team is adhering to the protocol, that data are being accurately recorded in the pCRFs, and that investigational product accountability checks are being performed.
- Perform source data verification (a comparison of the data in the pCRFs with the subject's medical records at the hospital or practice, and other records relevant to the study). This will require direct access to all original records for each subject (eg, clinic charts).
- Perform source verification of the genetic consent of participating patients and ensure that the investigational team is adhering to the specific requirements of this genetic research.

The monitor or another AstraZeneca representative will be available between visits if the investigator(s) or other staff at the centre need information and advice.

7.2 Audits and inspections

Authorised representatives of AstraZeneca, a regulatory authority, an Ethics Committee may visit the centre to perform audits or inspections, including source data verification. The purpose of an AstraZeneca audit or inspection is to systematically and independently examine all study-related activities and documents to determine whether these activities were conducted, and data were recorded, analysed, and accurately reported according to the protocol, Good Clinical Practice (GCP), guidelines of the International Conference on Harmonisation (ICH), and any applicable regulatory requirements. The investigator should contact AstraZeneca immediately if contacted by a regulatory agency about an inspection at his or her centre.

7.3 Training of staff

The principal investigator will maintain a record of all individuals involved in the study (medical, nursing and other staff). He or she will ensure that appropriate training relevant to

the study is given to all of these staff, and that any new information of relevance to the performance of this study is forwarded to the staff involved.

Before the first subject is entered into the study the investigational staff will have an opportunity to discuss the procedures associated with the collection of blood samples, extraction of DNA and genetic research with AstraZeneca personnel. The ethical considerations specific to genetic analysis and the importance of the informed consent process will be made clear. The requirements for the collections of the patients' samples will also be made clear.

7.4 Changes to the protocol

Study procedures will not be changed without the mutual agreement of the International Co-ordinating Investigator and AstraZeneca.

If it is necessary for the study protocol to be amended, the amendment and/or a new version of the study protocol (Amended Protocol) must be notified to or approved by each Ethics Committee, and if applicable, also the local regulatory authority, before implementation. Local requirements must be followed.

If an administrative change is required, such a change must be must be notified to or approved by each Ethics Committee according to local requirements.

If a protocol amendment requires a change to a particular centre's Informed Consent Form, then AstraZeneca and the centre's Ethics Committee must be notified. Approval of the revised Informed Consent Form by AstraZeneca and by the Ethics Committee is required before the revised form is used.

AstraZeneca will distribute amendments and new versions of the protocol to each principal investigator(s), who in turn is responsible for the distribution of these documents to his or her Ethics Committee, and to the staff at his or her centre. The distribution of these documents to the regulatory authority will be handled according to local practice.

7.5 Study agreements

The principal investigator at each centre must comply with all the terms, conditions, and obligations of the Clinical Study Agreement for this study. In the event of any inconsistency between this Clinical Study Protocol and the Clinical Study Agreement, the Clinical Study Protocol shall prevail.

7.6 Study timetable and end of study

Before a subject's enrolment in the study and any study-related procedures are undertaken the following should be fulfilled:

- Signed Clinical Study Protocol and other agreements between AstraZeneca and the Principal Investigator/Study Site.

- Approval of the study by the Ethics Committee
- Approval of the study, if applicable, by the regulatory authority.

The overall timetable for the study is summarised below:

Study period		Phase of development
Estimated date of first patient enrolled	April 2007	Phase I
Estimated date of last patient completed	August 2010*	

* End of study is defined as the point at which the last patient has received 6 months of treatment with AZD8330, or has withdrawn from the study (whichever is sooner).

In Part A of this study, patients may continue to receive AZD8330 until disease progression or as long as they continue to derive benefit from treatment. Therefore, the time at which the last patient stops treatment cannot be precisely predetermined. The study endpoint is defined as the point at which the last patient has received 6 months of treatment with AZD8330, or has withdrawn from the study (whichever is sooner). The study database will be locked at this point and the Clinical Study Report will be written. Serious adverse event reports for any patients still receiving treatment after the end of study will be entered on the AstraZeneca Global Patient Safety database. The study database will not be updated with this information nor an addendum to the Clinical Study Report be written.

8. ETHICS

8.1 Ethics review

AstraZeneca will provide Ethics Committees and Principal Investigators with safety updates/reports according to local requirements.

The final study protocol, including the final version of the Informed Consent Form, must be approved or given a favourable opinion in writing by an Ethics Committee as appropriate. The investigator must submit written approval to AstraZeneca before he or she can enrol any subject into the study.

The Principal Investigator is responsible for informing the Ethics Committee of any amendment to the protocol in accordance with local requirements. In addition, the Ethics Committee must approve all advertising used to recruit patients for the study. The protocol must be re-approved by the Ethics Committee annually, as local regulations require.

Where there is a genetic research, approval must be obtained for this genetic research and the associated genetic informed consent from the Ethics Committee. It must be clearly stated in

the approval that this genetic research is approved. The investigator must submit written approval to AstraZeneca before any subject participates in this genetic research.

For US only: The Principal Investigator is also responsible for providing the Institutional Review Board with reports of any serious and unexpected adverse drug reactions from any other study conducted with the investigational product. AstraZeneca will provide this information to the Principal Investigator.

Progress reports and notifications of serious and unexpected adverse drug reactions will be provided to the Ethics Committee according to local regulations and guidelines.

8.2 Ethical conduct of the study

The study will be performed in accordance with ethical principles that have their origin in the Declaration of Helsinki and are consistent with ICH/Good Clinical Practice, applicable regulatory requirements and the AstraZeneca policy on Bioethics.

For studies including genetic analysis special precautions are taken as described in Section 4.7.

8.3 Informed consent

The principal investigator(s) at each centre will ensure that the subject is given full and adequate oral and written information about the nature, purpose, possible risk and benefit of the study. Patients must also be notified that they are free to discontinue from the study at any time. The subject should be given the opportunity to ask questions and allowed time to consider the information provided.

The subject's signed and dated informed consent must be obtained before conducting any procedure specifically for the study, including the following:

- Collection of study blood samples
- Study ECGs
- Study Echocardiograms/MUGA scans
- Ophthalmological examination

Host Genetics Research will be covered separately in the informed consent forms, and all data protection and confidentiality principles, described in the main study protocol, are also applicable to the genetic research.

The principal investigator(s) must store the original, signed Informed Consent Forms. A copy of the signed Informed Consent Forms must be given to the subject.

If modifications are made according to local requirements, the new version has to be approved by AstraZeneca.

8.4 Patient data protection

The Master Informed Consent Form will incorporate (or, in some cases, be accompanied by a separate document incorporating) wording that complies with relevant data protection and privacy legislation. Pursuant to this wording, patients will authorise the collection, use and disclosure of their study data by the Investigator and by those persons who need that information for the purposes of the study.

The Master Informed Consent Form will explain that study data will be stored in a computer database, maintaining confidentiality in accordance with national data legislation. All data computer processed by AstraZeneca will be identified by randomisation code / study code / initials.

The Master Informed Consent Form will also explain that for data verification purposes, authorised representatives of AstraZeneca, a regulatory authority, an Ethics Committee may require direct access to parts of the hospital or practice records relevant to the study, including patients' medical history.

All data protection and confidentiality principles, described in the main study protocol, are also applicable to the genetic research.

Reference to participation in this genetic research should not be recorded into the patients' general medical records. All notes should be kept within the clinical study records.

Due to the exploratory nature of this genetic research, there will be no routine communication of results to patients. AstraZeneca will not provide individual genetic results to patients, any insurance company, any employer, their family members, general physician or any other third party, unless required to do so by law.

Extra precautions are taken to preserve confidentiality and prevent genetic data being linked to the identity of the subject, however, it must be recognised that there are exceptional circumstances where individuals may see both genetic data and a subject's personal identifier, for example in the case of a medical emergency, when AstraZeneca Physicians and investigators might know the patients' identity and might have access to the genetic data, or during regulatory audit where designated authorities must be permitted access to the relevant files.

